Expansion into a multi-site protocol: In its first year, the study experienced initial delays as the software necessary for IMT was upgraded to be compatible with newer versions of Windows as well as the VA system. Moreover, even after enrollment began, recruitment of systolic HF patients was more difficult than projected. In response to this challenge, the study will be expanded to multiple sites as well as home based exercise session, each with enhanced recruitment and adherence strategies. This change in study design coincides with [name] plans to transition to the VA Pittsburgh Healthcare System (VAPHS) which will be used to the advantage of the protocol design.

1. [name] will continue as PI of the overall trial as well as site PI at the (VAPHS). Four training arms (Aerobic vs. Strength vs. Combined aerobic-strength, vs. IMT) will be completed at VAPHS, along with pre- and post- skeletal muscle biopsies, bloodwork, DXA and functional assessments. 100 HF patients will be enrolled at that campus, drawing from its robust HF program as well as its extensive HF telehealth database (see recruitment strategies below).
2. The study will also continue at the VABHS where enrollment goals will be 50 HF patients. [name] will assume responsibility as the Boston site PI. Exercise randomization at the VABHS will be limited to aerobic vs. IMT, both to increase efficiencies for the reduced staffing available once [name] and members of his staff have departed for Pittsburgh, and also to ensure adequate enrollment to a RR&D SPIRE-funded 1 I21 RX001423-01A1 substudy (Exercise Training in HF: Structural and Functional Cardiac Remodeling [PI-[name]]) which will explore correlative effects of IMT vs. aerobic training on cardiac remodeling. Also, given [name] role as principal investigator in the ancillary SPIRE study of exercise effects on cardiac remodeling as well as the distinctive skillset required for the echo-based analysis of skeletal muscle perfusion (that is part of the original protocol), both the perfusion and remodeling ultrasound assessments will be studied exclusively at the VABHS. This too is a decision to help maximize local enthusiasm for the protocol, as it becomes a distinctive VABHS goal and responsibility.

Table 4: Outline of protocol (by visit)

Initial Assessment	Visit 1	Informed consent and physical exam, physical functional assessment battery (aerobic, strength, 6MWT, Hand Grip, gait speed, Sit to Stand, and questionnaires)

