	Visit 2 (within one week of visit 1)	Skeletal muscle biopsy; Serology and DXA scan Randomization
	Visit 3 (2-3 days after visit 2) (VABHS only)	Reassessment of biopsy site
Exercise Training	Visits 3/4-38/39	Exercise training sessions (3X/weekly; 60 minutes; 12 weeks)
Post assessment	Visit 39/40-41/43	Post-exercise assessment battery and additional group of assessments completed at visits 1 to 2/3

Table 5: Expansion to a Multi-Site Trial

	Recruitment goals	Exercise arms
VAMC Pittsburgh	100	Aerobic (35), Combined aerobic-strength (30 enrollees), IMT (35 enrollees)
VAMC Boston	50	Aerobic (25 enrollees); IMT (25 enrollees)

Total: 150 HF patients: Aerobic—60; IMT—60; Combined—30;

Study Population

• ***Study Population:*** 150 male and female systolic HF patients with mild-moderate symptoms while on optimal medical therapy will be enrolled. This target will allow for adequate power to address the study objectives even after accounting for a 20% drop-out rate due to attrition and/or suboptimal tissue samples for genetic analysis. Given the expansion to two campuses, and the variation in randomization at each site, the overall proportions of patients enrolled will vary from the original study design but still provide a sound statistical foundation for the anticipated analyses (see statistics section below).

• HF diagnosis will be contingent on a previous hospitalization for HF or physician assessment of HF associated. Each candidate will be examined at the time of enrollment by a cardiologist to ensure that he/she is clinically stable.

• ***Inclusion Criteria:***

- NYHA class II or III for the previous three months despite a minimum of 6 weeks of optimal treatment

- Age \geq 50 years

- Left ventricular EF (LVEF) (by echocardiogram or radionucleotide imaging study within 12 months of enrollment).

- Optimal therapy according to AHA/ACC and HFSA HF guidelines, including treatment with ACEI and beta-blocker therapy (for at least 6 weeks), or have documented reason for variation, including medication intolerance, contraindication, patient preference, or personal physician's judgment.

✓ Patients using aspirin (ASA) will be eligible, but asked to hold the medication for 48 hours prior to biopsy. This technique has previously been used with consistent safety. Patients will also be asked to avoid non-steroidal anti-inflammatory medications (NSAIDs) for 48 hours prior to the biopsy.

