General considerations: The analyses described below are of continuous outcome measures, primarily changes in function outcomes and gene expression and either continuous or categorical predictors. All analyses will be performed as general linear models. Potential confounders of each analysis will be outlined below and a 10% rule for evaluating confounders will be used, namely including a potential confounder if a 10% or greater change is seen in the main predictor effect. In all instances, outcome variables will be evaluated for violation of regression assumptions and transformation of these variables will be considered as a remedy if needed. Analyses will generally be performed with an intent-to-treat approach, with sensitivity analyses performed to assess the role of drop-outs on the results.

This grant examines a complex interplay of exercise regimens, gene expression and functional measures, resulting in a number of hypotheses that require testing. We are cognizant of the role of type I error in this and in interpreting results, focus will be placed on the overall results of these analyses and not on the results of individual tests. Thus, for example, significant relationships among gene expression outcomes and treatment categories as a whole will be considered as support for these hypotheses and isolated significant associations will not be unduly weighted in the interpretation of results.

Randomization will be generated using a SAS program based upon permuted random blocks of variable size to assure approximate balance over time and will be stratified by sex and statin use.

Validation of Study Measurements: At the start of the study, there will be two assessments of physical function battery. Intraclass correlations will be used to determine the relative repeatability of the various components of the battery. This information will be included in all manuscripts using these measures.

- *Aim 1. To assess differences in functional outcomes (peak VO₂, 1RM) relative to the training therapy:*

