a) *Aerobic vs. Strength vs. Aerobic-Strength regimens will be compared to one another b) Inspiratory Training will be compared to Aerobic-Strength:* In this aim, we compare the combined aerobic-strength training regimen to the single-therapy regimens of aerobic training and strength training, as well as the inspiratory training regimen. These comparisons will be made with changes in the functional outcomes (peak VO₂, 1RM) from baseline as the continuous outcome measures in separate models and training regimen as the categorical predictor in a general linear model, with the following factors considered as potential confounder variables: age, sex, and comorbidities. To limit the type I error rate, only the pre-planned comparisons of the combined aerobic-strength training to the other regimens will be considered. In addition, secondary analyses will consider the following aerobic, strength and inspiratory variables as outcome variables in similar analyses to those outlined above: 6MWT, sit-to-stand, and hand grip strength.

- **Aim 2. To assess gene expression and skeletal muscle perfusion in relation to the different training regimens:** In this aim, we examine the change from baseline to post-exercise regimen in the expression of proteolytic (FoxO and Ubiquitin) and anti-proteolysis (IGF-1 and PGC-1 α) genes as predictors of the change in functional outcomes (peak VO₂, 1RM) over the same period. Separate general linear models for each functional outcome will be performed with gene expression changes as the primary predictor and the following variables considered as potential confounders: age, sex, and comorbidities. As above, a 10% rule for introducing confounding variables and the transformation of outcome variables to deal with regression assumption violations will be considered.

Treatment regimens will also be categorized as those with and without direct skeletal muscle stimulation and this categorical variable will be considered as a predictor of a change in the expression of proteolytic and anti-proteolysis genes in general linear models in a similar fashion to that described above. In addition, similar general linear models will be used with changes in skeletal muscle perfusion as a continuous outcome and aerobic and inspiratory training vs. strength-only training as a categorical predictor with similar potential confounders as noted above.

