Secondary analyses will include assessment of the relative impact of changes in skeletal gene expression vs. changes in perfusion dynamics as predictors of changes in function and quality of life as outcomes. Measures of changes from baseline in serum inflammation, cytokines, and adipokines, and effects of muscle histology will be included as covariates in these analyses. General linear models will be used (outlined above).

Sample size/Power: In this study, we plan to recruit 210 individuals and assign them to one of 4 treatment arms, i.e., randomized between aerobic, aerobic strength, and IMT in VAPHS and between aerobic and inspiratory muscle training in Boston. Sample size calculations are based on 20% attrition over the course of the study. In general, a sample size of 40 per group, using a t-test of independent samples as a simplified model, results in an effect size of 0.64 SD units for 80% power, using a two-sided alpha of 5%.

- **Aim 1:** For this aim, we present calculations for detecting differences in peak VO₂. Previous work by Becker (108) shows a $2.1 \text{ mL O}_2 \cdot \text{kg}^{-1} \cdot \text{min}^{-1}$ change in peak VO₂ in a 6 month aerobic-strength training regimen. Similarly, Tyne-Lenne, et al. shows a $1.1 \text{ mL O}_2 \cdot \text{kg}^{-1} \cdot \text{min}^{-1}$ change in a strength-only regimen (109), HF-ACTION (85) shows a $0.6 \text{ mL O}_2 \cdot \text{kg}^{-1} \cdot \text{min}^{-1}$ change in an aerobic regimen and the IMT trial by Dall'Ago et al. (12) shows a $4 \text{ mL O}_2 \cdot \text{kg}^{-1} \cdot \text{min}^{-1}$ change with inspiratory training. Standard deviations [SD] of the change in peak VO₂ over an exercise regimen are not directly available but using interquartile range values from the largest study [HF-ACTION, n=1442], we obtain a SD value of 2.2 for a 3-month intervention. This would correspond to detecting a difference of $1.26 \text{ mL O}_2 \cdot \text{kg}^{-1} \cdot \text{min}^{-1}$ in any comparison with 80% power, assuming a SD=2.2.

- **Aim 2:** In a similar fashion, a simplified comparison of those with gene expression below the median vs. those above the median would be able to detect a difference of $1.26 \text{ mL O}_2 \cdot \text{kg}^{-1} \cdot \text{min}^{-1}$ in peak VO₂ with 80% power. Analyses of combined training groups facilitates capacity to detect smaller differences between groups.

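### Combined training enters every pre-planned Aim 1 contrast but has the fewest patients; a 30/40/30 split at Pittsburgh, with site in the model, is a cheap improvement

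*Combined protocol and SAP*

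**What the plan says.** Table 5 (Expansion to a Multi-Site Trial) allocates Pittsburgh's 100 patients as "Aerobic (35), Combined aerobic-strength (30 enrollees), IMT (35 enrollees") and Boston's 50 as "Aerobic (25 enrollees); IMT (25 enrollees"). The line beneath it gives "Total: 150 HF patients: Aerobic—60; IMT—60; Combined—30".

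The section on expansion into a multi-site protocol states that "Exercise randomization at the VABHS will be limited to aerobic vs. IMT". It gives two reasons: reduced Boston staffing and enrolment to a substudy comparing those two regimens. It gives no reason for the 35/30/35 split at Pittsburgh. The Study Population text acknowledges that the arm proportions have changed, calls them statistically sound and refers to the statistics section.

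In that section, Aim 1 states that "only the pre-planned comparisons of the combined aerobic-strength training to the other regimens will be considered". The listed candidate covariates are age, sex and comorbidities; site is not among them. The Sample size/Power paragraph uses "a sample size of 40 per group, using a t-test of independent samples as a simplified model", which it says "results in an effect size of 0.64 SD units for 80% power, using a two-sided alpha of 5"%. It applies this to every comparison and gives no calculation for 30 against 60.

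**The concern.** When one arm is the common member of every planned contrast, its size does most to set their precision. Boston already adds 25 aerobic and 25 IMT patients and no combined patients. Pittsburgh is the only place where that could be offset, and its split adds to the imbalance instead. At stake is precision on the trial's own main question, which the same 150 patients could answer somewhat better.

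A second matter follows from the layout. Every combined patient is at Pittsburgh, while 25 of 60 (42%) of each comparator arm is at Boston. A pooled contrast without site therefore mixes the randomised Pittsburgh comparison with a non-randomised comparison across sites.

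**Working it through.** **Inputs.** Allocations from Table 5. From Sample size/Power: 20% attrition, SD of change in peak VO2 of 2.2, two-sided 5%, stated difference 1.26 mL/kg/min. The same paragraph gives mean changes of 2.1 (combined), 0.6 (aerobic) and 4 (IMT), which imply gaps of 2.1 − 0.6 = 1.5 and 4 − 2.1 = 1.9. I take the 20% loss as equal across arms and sites.

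**The plan's own figure.** With 40 per group, SE = √(2/40) = 0.2236 SD. A two-sample t-test has 80% power at 0.634 SD, so the stated 0.64 is reproduced. In peak VO2 units, 0.64 × 2.2 = 1.41, not 1.26. Power at 1.26 with 40 per group is 72%. The 1.26 fits about 48 per group, which under Table 5 is aerobic versus IMT (60 × 0.8 = 48 each), not a combined contrast.

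**Evaluable patients (× 0.8), aerobic/combined/IMT.**
- Current: Pittsburgh 28/24/28, Boston 20/0/20.
- Proposed (Pittsburgh 30/40/30 enrolled): Pittsburgh 24/32/24, Boston 20/0/20.

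**Variance factors.** Let c be combined, a the Pittsburgh patients per comparator arm, and b the Boston patients per comparator arm. The variance of a combined contrast is 2.2² times one of the following.
- Pooled, no site: 1/c + 1/(a+b).
- Additive site term: 1/c + 1/(a+b) + b/[2a(a+b)]. The last term is the price of estimating the site effect from the aerobic and IMT arms.
- Pittsburgh only: 1/c + 1/a.

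With site:
- current: 1/24 + 1/48 + 20/(2×28×48) = 0.0417 + 0.0208 + 0.0074 = 0.0699
- proposed: 1/32 + 1/44 + 20/(2×24×44) = 0.0313 + 0.0227 + 0.0095 = 0.0634

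Pooled: 0.0625 to 0.0540. Pittsburgh only: 0.0774 to 0.0729.

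**Power.** SE = 2.2 × √factor; noncentral t with 116 df (site), 117 (pooled) or 77 (Pittsburgh only). By symmetry the results are the same for combined versus aerobic and combined versus IMT.

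| Analysis | SE, current → proposed | Power at 1.26 | Detectable at 80% |
|---|---|---|---|
| Site in model | 0.582 → 0.554 | 57% → 62% | 1.64 → 1.57 |
| Pittsburgh only | 0.612 → 0.594 | 53% → 55% | 1.74 → 1.69 |
| Pooled, no site | 0.550 → 0.511 | 62% → 69% | 1.55 → 1.44 |

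With site, power at 1.5 (combined versus aerobic) rises from about 73% (72.5%) to 77%, and at 1.9 (combined versus IMT) from 90% to about 93% (92.5%). In patients, the current ratio would need about 150 × 0.0699/0.0634 = 165 to match the proposed site-adjusted precision.

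**What is given up.** Aerobic versus IMT goes from 48 to 44 evaluable per arm. Its factor rises from 2/48 = 0.0417 to 2/44 = 0.0455, and its power at 1.26 falls from 80% (79.5%) to 76%.

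**A heavier shift.** Pittsburgh 25/50/25 gives 62.2% with site against 61.6% for 30/40/30, 54.2% against 55.4% on Pittsburgh alone, and 72% against 76% for aerobic versus IMT.

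**The case against.** The main source of the imbalance is Boston's two-arm design, which the protocol explains. The changed proportions are acknowledged, neither allocation reaches 80% at 1.26, and the secure gain is about 4 to 5 points. All of that stands, and it keeps this a modest recommendation. It does not explain the Pittsburgh split, which is the only part proposed for change.

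Three stronger readings are tempting, and the documents do not support them.
- A reader might infer that Pittsburgh should go to 25/50/25, restoring 40 evaluable per arm and lifting pooled power from 62% to 72%. That gain leans on the cross-site comparison. With site in the model the heavier shift adds 0.6 points over 30/40/30, it does worse on Pittsburgh alone, and it costs 4 more points on aerobic versus IMT. Without a site term it would also raise Boston's share of the comparator arms from 42% to 50%.
- A reader might infer that the 40 per group came from 150 patients in three equal arms (50 × 0.8 = 40). The same paragraph speaks of 210 patients in four arms, and 210/4 × 0.8 = 42 is also close. The plan does not derive the figure.
- A reader might infer that 35:30:35 cannot work with "permuted random blocks of variable size". Table 5 states recruitment goals, not a randomisation ratio; the statistics section promises only approximate balance; and no stratum sizes are given.

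**Conclusion.** The point holds as a low-cost improvement worth considering, not as a flaw that invalidates the design. The arm on which both allocated Aim 1 contrasts depend is the smallest, and Pittsburgh's split adds to the shortage. The figure to rely on is the site-adjusted one: 57% to 62% at 1.26, with a variance about 9% lower (0.0699 to 0.0634).

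This rests on the plan's SD of 2.2, equal 20% loss in all arms, a site effect that is the same across arms, and the new ratio applying from the first patient. The expansion section says that enrolment had already begun before the expansion, so the achievable gain may be smaller; the documents do not say how many patients remain.

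It also rests on the three-arm, 150-patient plan in Overall Study Protocol and Table 5. The expansion section and Aim 1 also name a strength-only arm, and Sample size/Power gives 210 patients and four arms. If a strength-only arm is to run, 30/40/30 leaves it no Pittsburgh patients and there would be a third combined contrast.

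**What to change.** 1. Reconcile the number of arms and the total sample size first.
2. If the three-arm, 150-patient plan stands, set Pittsburgh to aerobic 30, combined 40, IMT 30 (3:4:3) on a Pittsburgh-only list. Leave Boston at 25/25. Totals become aerobic 55, combined 40, IMT 55.
3. Put site in the Aim 1 model as a fixed term rather than leaving it to the 10% confounder rule. This matters under either allocation; under the new one Boston's share of each comparator arm becomes 25/55 (45%). Report the Pittsburgh-only contrast as a sensitivity analysis.
4. If patients are already randomised, apply the new ratio only to the remaining Pittsburgh patients and adjust for allocation period, so that a time trend is not read as an arm difference.
5. Restate power for the actual combined contrasts.

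The cost is a new Pittsburgh list, revised wording in Table 5 and Aim 1, and about 4 points of power for aerobic versus IMT. No extra patients are needed, and Boston's 25/25 allocation, which feeds the substudy, is untouched.

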- **Cardiopulmonary Exercise Testing:** Treadmill exercise testing in association with air-gas-exchange, generally considered to be an optimal gauge of aerobic capacity (92), will be supervised by [name] at VAPHS, and Drs [name] and [name] in VABHS. All these physicians have supervised large numbers of studies over many years. Furthermore, [name] has employed the technique in multiple research investigations (HF-ACTION, Tai Chi Mind Body Exercise for HF, and most recently for the VA based pilot study for this proposal) and brings his perspective and sophistication to the broader study team. Similar expertise exists on each study campus.

A motor-driven treadmill will be used to generate the exercise stimulus. A modified Balke protocol will be utilized. A lightweight disposable pneumotach device will be positioned in the enrollee's mouth during the exercise for gas exchange assessments (MedGraphics Ultima or equivalent system). Peak VO₂, VAT, the VE/VCO₂ slope, and respiratory exchange ratio (RER) will be measured, as well as hemodynamics (max heart rate [HR] and blood pressure [BP]), time, and ECG waveforms). Any abnormalities will be reported to the patient's cardiologist and primary care physician; continued participation in the study will require physician clearance.

Both the Borg Rate of Perceived Exertion (RPE) (93) and the Modified Borg Scale for Perceived Dyspnea (Shortness of Breath) will be completed during the CPX and the 6MWT to quantify exercise associated symptoms before and after the test.

All CPX test data will be analyzed and validated by Drs. [name] and [name] and a CPX core lab will be organized at the VAPHS.

- **Six Minute Walk Test:** The 6MWT is also a commonly used assessment of aerobic capacity and submaximal endurance in HF patients. As a measure of everyday walking activity, it is often felt to complement the insights

afforded by CPX indices. Using standard methodology described by the American Thoracic Society (94), patients will be asked to walk back and forth along a 30 meter course as quickly as possible for 6 minutes. A supervising exercise physiologist will encourage patients to walk as quickly as possible. The test will be scored in meters walked in 6 minutes, rounding to the nearest meter. As noted, the Borg Rate of Perceived Exertion (RPE) and the Modified Borg Scale for Perceived Dyspnea (Shortness of Breath) will be completed during the 6 minute walking test (and CPX).

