Skeletal Muscle Analyses: Since the study's original funding, the VA Boston established its own laboratory facility for skeletal muscle research. [name], a VA investigator, and his laboratory staff will complete all skeletal muscle gene expression analyses. [name], an investigator from Beth Israel Deaconess Hospital, will no longer conduct PCR analyses but will remain on the study staff for his analytic insights. The analyses will center on genes previously defined as induced or suppressed in atrophying skeletal muscle (atrogenes) (35).

- **Atrogenes:** We will analyze gene sequences that code for skeletal muscle atrophy in the muscle biopsy specimens from HF patients and controls. As discussed above, these genes belong to a specific set of atrophy genes, aka atrogenes, which we previously characterized to be regulated in several models of skeletal muscle atrophy (35). We will particularly focus on FoxO, PSMA1 and GLUL, PGC1 and IGF-1 because our pilot studies defined significant differences in expression of these genes and correlations with muscle function in HF patients, but genes within all the following functional groups will also be analyzed:

1. **Protein degradation atrogenes:** atrogin-1/MAFbx, MuRF-1, Polyubiquitin (UbB UbC), proteasome subunits (PSMA1), cathepsin L.
2. **Growth factor pathways (molecular signaling related to growth):** PGC-1 α , FNDC5 (irisin), IGF-1, IGFBP5, FoxO1, FoxO3, myostatin, follistatin.
3. **Metabolic atrogenes,** lactate dehydrogenase, glutamine synthase.

- mRNA extraction and rtPCR: Total skeletal muscle mRNA will be extracted from muscle biopsies using Trizol reagent and well established protocols. Typically 5-10 μ g of total RNA is obtained from approximately half of a biopsy specimen. Samples will be stored in nuclease-free water at -80C. Total RNA will be converted to cDNA by reverse transcription using SuperScriptII reverse transcriptase (Stratagene) in standard reactions according to the manufacturer's recommendations.

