mRNA levels will be determined by real-time PCR using the Applied Biosystems® StepOne real-time PCR analyzer. Multiplexed amplification reactions will be performed using GAPDH as an endogenous control (GAPDH primers/VIC-labeled) using the TaqMan One Step PCR Master Mix reagents Kit (#4309169, Applied Biosystems). Probes/primers for the specific genes to be analyzed will be purchased directly from Applied Biosystems. The following amplification settings will be used: Stage 1 (reverse transcription): 48°C for 30 min; Stage 2 (denaturation): 95°C for 10 min and Stage 3 (PCR): 95°C for 15 sec and 60°C for 60 sec for 40 cycles. The Ct (Threshold cycle) values for each reaction will be transferred to a Microsoft Excel spreadsheet and calculation of relative gene expression will be performed from this data according to published algorithms (TaqMan Cytokine Gene Expression Plate 1 protocol, Applied Biosystems). All RNA samples will be analyzed in triplicate, with the mean value used in subsequent analyses.

Of note, in our pilot studies, biopsy data was initially evaluated on different 96-well plates to allow biopsy processing before the completion of the study; however, this was associated with high variability and poor precision. Analyses were then repeated with all of the biopsy samples on the same plate. This technique strengthened our analysis and revealed key differences and correlations between gene expression and function. In this proposed study, we shall prepare and store cDNA from the muscle biopsies in small groups as the biopsies are performed, and then perform rtPCR analyses batched by exercise arm in order to minimize plate-to-plate variation in the rtPCR data.

- **Microscopic Analyses:** [name] and a consulting microscopy technician will complete all light microscopic analyses at the Boston VA. [name] has an extensive track record of skeletal muscle phenotypic analysis. Both he and his laboratory staff will work directly with [name] to ensure the phenotypic assessments are completed in the most useful fashion. Given the controversial perspectives regarding the effects of disease vs.

deconditioning on skeletal muscle physiology and function, the attention to phenotypic assessments will be prioritized as a vital perspective relative to gene expression patterns and serologic assessments of inflammation.

- Muscle Tissue Histology and Morphometric Assessments

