Study Data Management and Quality Control: Prior to the initiation of the study, all investigators and research staff involved in clinical activities will meet to review study procedures and will complete all required trainings on data and patient privacy procedures. Documentation of any protocol breaches will be required. Each protocol violation will be evaluated by the principal investigator, and a determination made regarding the validity of any justification for the violation.

The clinical database with all research data will be stored on VA network drives and housed behind the VA firewall on VA owned and maintained servers, which are backed up on a regular schedule. All computers will have Kerberos passwords and come equipped with antivirus software. Data will not be stored on desktops or on non-VA servers. Study data will be coded with a unique study identifier for each participant and stored in a de-identified manner. A study data set without identifiable information will be used for all data analysis. Identifiable information will be collected for patient tracking and safety purposes, but will only be kept for as long as the study is active. De-identified clinical data will be stored separately from the participant's name, contact information, and real SSN. Access to the cross-walk file linking the participant's identifiers and their study data will be restricted to the project manager. This file will be destroyed according to CSP policy after the study ends. Study data will be retained and stored after the study ends according to federal and local VA regulations. Access to the study data is heavily restricted to individuals with approval from the principal investigator to access the data. Individuals must be properly credentialed research staff and must be compliant with VA security trainings (i.e., Research Data Security, HIPAA and VA Privacy Training, Cyber-Security, and Good Clinical Practices).

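### Batching rtPCR by exercise arm aligns plate variation with the regimens that Aim 2 compares; mix arms on plates, and state masking for the central CPX and histology readers

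*Combined protocol and SAP*

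**What the plan says.** **PCR.** Under Skeletal Muscle Analyses, one VA Boston laboratory does all the assays: the lead investigator there "and his laboratory staff will complete all skeletal muscle gene expression analyses". The mRNA extraction and rtPCR text gives the pilot history. There, "biopsy data was initially evaluated on different 96-well plates", which gave imprecise results; the remedy was that "Analyses were then repeated with all of the biopsy samples on the same plate". For this trial, cDNA is stored as biopsies arrive, and the laboratory will then "perform rtPCR analyses batched by exercise arm in order to minimize plate-to-plate variation in the rtPCR data". Each RNA sample is run three times and averaged, with GAPDH as the internal control. No layout rule says where a patient's baseline and post-training samples go.

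**Use of the PCR data.** Aim 2 models change in expression in two ways: as a predictor of change in peak VO2 and 1RM, and as an outcome compared between regimens that load skeletal muscle directly and those that do not. No model includes plate or batch.

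**Other central reads.** Two investigators analyse and validate the CPX tests, and "a CPX core lab will be organized at the VAPHS". Light microscopy is done at the Boston VA and covers fibre area together with tissue damage, inflammation and wasting. Neither section mentions masking.

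**Coding.** Under Study Data Management and Quality Control, "Study data will be coded with a unique study identifier for each participant", analysis uses a file without identifiers, and the linking file is restricted to the project manager. This is written as a privacy measure; arm and visit are not mentioned.

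**The concern.** The laboratory has already seen plate-to-plate variation large enough to make it repeat the pilot assays on one plate. Batching by arm tightens comparisons within an arm, but the Aim 2 regimen comparison is between arms. With every plate belonging to one arm, any plate effect left in the change score is inseparable from a regimen effect. Plate cannot then be fitted as a fixed factor beside arm, because plate determines arm. The other Aim 2 model is exposed as well: a batch shift shared by an arm can create or hide an association between expression change and functional change if the arms also differ in function.

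A change score protects against an additive plate shift only when both of a patient's samples are on the same plate. The plan does not require this.

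A lesser question concerns the reads that involve judgement. Histological grading does, and so, in my technical view, does locating the ventilatory threshold on a CPX record. A reader who knows the arm or the visit can shift such values without intending to, and the plan does not say what the readers will know.

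**Working it through.** The plan gives no figure for plate variation or reader bias, so there is nothing of its own to reproduce. The layout follows from stated numbers; the error rates rest on assumed effect sizes.

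**1. Does an arm fit on one plate?**
- Inputs: 60 aerobic, 60 IMT and 30 combined (Table 5 and the total beneath it); two visits; triplicate runs; 96 wells as in the pilot. The main study's plate size is not stated, so 96 is an assumption. GAPDH is multiplexed in the same well.
- Wells per gene = patients × 2 × 3. For 30 patients: 180 (180/96 = 1.9 plates). For 60: 360 (3.75 plates).
- After 20% attrition: 24 × 6 = 144 (1.5 plates) and 48 × 6 = 288 (3 plates).

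No arm fits on one plate, before or after attrition. The statistics section gives 210 patients instead of 150; a larger total would only add plates.

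**2. Would mixing arms need more plates?**
- A full plate holds 96/6 = 16 patients with both visits, before any control wells.
- By arm: 60/16, 60/16 and 30/16 round up to 4 + 4 + 2 = 10 plates per gene. Mixed: 150/16 rounds up to 10.
- Completers by arm: 3 + 3 + 2 = 8. Mixed: 120/16 rounds up to 8.

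The plate count is the same.

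**3. Illustration: plate effects aligned with arm.**
- Contrast: combined against one other arm, 24 against 48 completers. Aim 2 does not list which regimens fall in its two categories, so this pair is an example.
- In patient-SD units the variance of the difference is 1/24 + 1/48 = 0.0625 (SE 0.25).
- Let τ be the assumed SD of the residual plate effect in the change score. With one independent effect per arm, the true variance is 0.0625 + 2τ². The actual two-sided error of a nominal 5% test is 2Φ(−1.96 × √[0.0625/(0.0625 + 2τ²)]).
- With independent effects per plate, on 2 and 3 plates, 2τ² becomes τ²(1/2 + 1/3) = 0.833τ². This is approximate, because some plate variation would then also enter the estimated SD.

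| τ (patient SD) | One effect per arm | One effect per plate |
|---|---|---|
| 0.1 | 8.8% | 6.6% |
| 0.2 | 19% | 11% |
| 0.3 | 32% | 19% |

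If both visits share a plate and the shift is purely additive, τ is 0 and the error rate stays at 5%.

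**4. Illustration: a shift in CPX reading.**
- SD of change in peak VO2 is 2.2 (Sample size/Power), so SE = 2.2 × 0.25 = 0.55 mL/kg/min.
- For an assumed shift b in one arm, error = Φ(−1.96 + b/0.55) + Φ(−1.96 − b/0.55).
- b = 0.1: b/SE = 0.18, error 5.4%. b = 0.2: 0.36, 6.5%. b = 0.3: 0.55, 8.5%.
- Against the plan's detectable difference of 1.26, b = 0.1 is 8% and b = 0.3 is 24%. The 1.26 is a detectable difference, not an expected one.

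**The case against.** **PCR is an instrument read-out.** Threshold cycles come from the analyser, pass through published algorithms and are averaged over three runs, with GAPDH in the same reaction. This stands against any claim that PCR is a judgement-based outcome, and GAPDH may absorb part of a plate shift. It does not answer the plate problem. Triplicates on the same plate share its effect, and the plan itself treats plate variation as something still to be controlled. It also means that coding the samples alone would not help: coded samples still run arm by arm remain confounded.

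**The laboratory need not know the arm.** A reader might infer from batching by arm that it does. That does not follow, since someone else could assemble coded batches.

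**The plan is silent on masking; it does not say readers are unmasked.** This stands. Part of the text just before the statistical section was also unavailable. The supportable statement is that masking is not stated.

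**The test itself is the larger exposure.** Peak VO2 and 1RM depend on effort and on-site supervision, and no central read of 1RM is described. This stands and limits what central masking can achieve. The 6MWT text says "A supervising exercise physiologist will encourage patients to walk as quickly as possible", but that outcome is secondary and follows a cited standard method. The 1RM follows a set four-stage procedure. A separate request for scripted encouragement would add little.

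**The bias sizes are assumed.** They are. At the low end of the CPX range the inflation is negligible (5.4%).

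**Conclusion.** The PCR point holds on the plan's own wording. Arm-wise batching places a source of variation that the investigators have already met between the groups that Aim 2 compares, and an arm does not fit on one plate if plates have 96 wells. The size is unknown. The 6.6% to 32% error rates rest on an assumed residual plate SD of 0.1 to 0.3 patient SD, 24 against 48 completers, and samples whose plate effects do not cancel in the change score.

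The masking point is smaller: the plan should state what CPX and histology readers know. The 5.4% to 8.5% range is illustrative only.

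A reader might go further and conclude that the central readers are known to be unmasked, that coding would cure the PCR problem, or that masking is free of staffing cost. The documents support none of these. They do not discuss the cost of masking or reject it on staffing grounds, and they identify no regimen that readers favour. The change is worth making before the assays are run, because the confounding cannot be removed by analysis afterwards.

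**What to change.** 1. Replace batching by arm with plates that mix the arms in a balanced or randomised layout. For each gene, keep a patient's baseline and post-training samples on the same plate.
2. Include plate as a factor in the Aim 2 expression models.
3. Send CPX files and histology slides to the existing central readers under codes that hide arm and visit, building on the present study identifiers and the linking file held by the project manager. State in the CPX and microscopy sections that readers are masked.
4. Acknowledge that central masking leaves effort and supervision effects on peak VO2 and 1RM untouched.

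Cost: protocol and procedure wording, a plate map, and slightly more sample and data handling. On the count above, the number of plates does not change. The existing coding suggests that the extra work is small, but the documents give no estimate.
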